GROUP 3: Treatment as Usual (TAU) To establish a baseline comparison for treatment effects, participants in the TAU arm will not receive contact with a study social worker, will not receive education or fact sheet information, and will be asked to continue with their lives as they normally would. Similar to groups 1 and 2, TAU participants will complete the self-report surveys as described below.

Additional study information:

Outcome Data (GPS/diary): To objectively measure community activity and participation behavior, we will collect a combination of Global Position System (GPS) data, in conjunction with daily self-report travel diaries from a sub-set of participants (**Appendix 27, 38**).

Of the 600 individuals enrolled in the study, a subset of participants (N=100 per arm; 300 total) will be invited to a one week GPS/diary study component at two time points (at baseline and again at the 12-month assessment). Participants will be mailed a cover instruction letter, along with the portable GPS data logger (such as, QStartz BT Q1000XT GPS logger), 1 weeks' worth of paper daily travel diaries (**Appendix 27**), and an additional GPS letter with notes for completing the week of GPS data logging (**Appendix 30**). Participants will also be given the option of completing the Travel Log electronically. Participants who wish to complete the travel log electronically will be emailed an excel version of the travel log (**Appendix 38**) in addition to the paper version.

- The GPS device is small (72 x 47 x 20mm; 64.g) and can be attached with Velcro to a belt or wheelchair, or can be placed in a pocket, purse, backpack, etc. This portable device works up to 24 hours on a single charge when set at a 15 sec epoch acquisition. Participants will be provided with a charger and instructed to charge the device nightly, power them on in the morning, wear them during waking hours, and remove them at bed time. Participants will be told to go about their daily routine as they normally would.

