Per sponsor request, we will have a Certificate of Confidentiality (CoC) in place prior to beginning GPS/diary data collection.

Outcome Data (Self-report Surveys): All 3 groups will complete a baseline (prior to intervention), 3-month (mid-intervention), 7-month (post-intervention), and 12-month survey (See **Appendix 8** for Survey and **Appendix 13** for baseline cover letter and **Appendix 14** for follow-up cover letter). The survey will be available online. It will also be available on paper if the participant prefers or administered via telephone if there are accessibility issues (**Appendix 8**).

EW-D Survey Data: Participants in the EW-D arm (group 1) will complete an additional survey designed to assist the Wellness Coach with tailoring the intervention sessions (**Appendix 9**). Participants will complete it at baseline (prior to intervention), 3-month (mid-intervention), 7-month (post-intervention), and 12-month survey. Participants will complete the survey on paper and the de-identified survey responses will be entered and stored on the Sound Generations network (the data will allow Sound Generations to accrue supporting data for their intervention). It may also be administered via telephone if there are accessibility issues.

Missing data/survey: For both the self-report survey and the EW-D survey, after research staff receive the completed survey, they will review it and contact the participant if there is any missing data using the missing data script (**Appendix 15**). Research staff will attempt to contact the participant up to 3 times for missing data. This script will also be used to remind participants about unreturned surveys and consent forms.

Withdrawal from study:

Participants who are withdrawn by study staff: We will withdraw enrolled participants who are unreachable after multiple attempts. Participants who have been non-responsive (attempted to contact them (via phone or email) no fewer than 3 times and no more than 6 times over a 4-week period) to attempts by research staff and the wellness coach to schedule visits or follow up on survey mailings will be withdrawn from this study (**Appendix 12**). During our last few contact attempts, we will let participants know that we'll conclude their participation if we do not hear back within 2 weeks. They will also be notified that if they would like to re-join the study, then they can contact us at their convenience.

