Participants who chose to withdraw themselves: When a participant chooses to withdraw from the study, study staff will attempt to contact participants (via phone or email) to assess for any Adverse Events or Serious Adverse Events. Study staff will ask participants if their withdrawal was related to any study activities and will collect any information necessary to complete an Adverse Event Report as outlined in the DSMP (**Appendix 19**). Study staff will also ask the participant (via phone or email) if they would be willing to continue completing any aspect of the study going forward, such as the study surveys (**Appendix 32**). If participants request no further contact with study staff when withdrawing, study staff will cease communication with the participant.

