10.5 Data and Safety Monitoring. A Data and Safety Monitoring Plan (DSMP) is required for clinical trials (as defined by NIH). If required for your research, upload your DSMP to the **Supporting Documents** SmartForm in **Zipline**. If it is embedded in another document you are uploading (for example, a Study Protocol, use the text box below to name the document that has the DSMP.

DSMP (Appendix 19) has been uploaded.

10.6 Un-blinding. If this is a double-blinded or single-blinded study in which the participant and/or you do not know the group to which the participant is assigned: describe the circumstances under which un-blinding would be necessary, and to whom the un-blinded information would be provided.

n/a

10.7 Withdrawal of participants. If applicable, describe the anticipated circumstances under which participants will be withdrawn from the research without their consent. Also, describe any procedures for orderly withdrawal of a participant, regardless of the reason, including whether it will involve partial withdrawal from procedures and any intervention but continued data collection or long-term follow-up.

We will withdraw enrolled participants who are unreachable after multiple attempts. Participants who have been non-responsive (attempted to contact them (via phone or email) no fewer than 3 times and no more than 6 times over a 4 week period) to attempts by research staff and the wellness coach to schedule visits or follow up on survey mailings will be withdrawn from this study (Appendix 12). During our last few contact attempts, we will let participants know that we'll conclude their participation if we do not hear back within 2 weeks. They will also be notified that if they would like to re-join the study, then they can contact us at their convenience.

10.8 Anticipated direct benefits to participants. If there are any direct research-related benefits that some or all individual participants are likely to experience from taking part in the research, describe them below:

Do not include benefits to society or others, and do not include subject payment (if any). Examples: medical benefits such as laboratory tests (if subjects receive the results); psychological resources made available to participants; training or education that is provided.

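### Staff may stop after anything from 3 to 6 contact attempts, with no rule keeping the number equal across arms, so survey follow-up could differ by arm; the likely bias is small.

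*Protocol*

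**What the plan says.** Protocol 5.1 (Withdrawal from study) has staff withdraw enrolled participants who cannot be reached by phone or email after attempts made "no fewer than 3 times and no more than 6 times over a 4-week period". Section 10.7 repeats the rule: "no fewer than 3 times and no more than 6 times over a 4 week period". It applies to people who do not answer attempts "by research staff and the wellness coach to schedule visits or follow up on survey mailings will be withdrawn from this study". In the last few attempts the participant is told that participation will end without a reply within 2 weeks, and that re-joining is possible on the participant's own initiative.

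The preceding paragraph of 5.1 (Missing data/survey) starts from the point at which a completed survey has been received. It says: "Research staff will attempt to contact the participant up to 3 times for missing data". It then adds: "This script will also be used to remind participants about unreturned surveys and consent forms". No number of attempts is given for that second use.

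On arm knowledge, the un-blinding question in 10.6 is answered as not applicable, and no blinding of follow-up staff is described elsewhere. Sessions exist only in the EW-D and wellness education arms; "participants in the TAU arm will not receive contact with a study social worker". For those who withdraw themselves, 5.1 has staff ask "if they would be willing to continue completing any aspect of the study going forward, such as the study surveys". No such offer is written for participants whom staff withdraw.

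The SAP (Statistical Approach) declares intent-to-treat and tests change scores by ANOVA. It states no missing-data method or sensitivity analysis.

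**The concern.** The number of attempts is a range whose top is twice its bottom. Staff could follow the protocol to the letter while giving one arm consistently more attempts than another. The people recovered by the fourth to sixth attempt may well differ from prompt responders. If they are recovered more often in one arm, the observed samples differ in a way that randomization does not protect against. A change score needs an observed follow-up, so with no missing-data method stated, retention procedures are the main safeguard for the comparison.

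The design makes unequal contact plausible. Coach attempts and session scheduling arise only in the two session arms, yet failing to respond to them can end participation in the whole study, surveys included. In the TAU arm only survey follow-up applies.

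**Working it through.** **Reading the two paragraphs together.** The limit of 3 is attached to missing data in a survey already received. The withdrawal rule concerns people who do not respond at all. Only the script is said to be reused for unreturned surveys. If the limit travels with the script, it conflicts with a fourth, fifth or sixth attempt. If it does not, the rules cover different situations. The text does not settle which.

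**Inputs from the documents.** Attempts: minimum 3, maximum 6. Sample: 600 in three arms, so 600/3 = 200 per arm if allocation is equal (an assumption, in line with the equal group maxima of 250 in Protocol 2.7). The documents give no contact rate, dropout rate or SD, so there is no planned figure to reproduce.

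**Assumed inputs.**
- p, the chance that one attempt reaches a non-responder: 0.2 to 0.4, attempts independent.
- f, the share of an arm needing to be chased: 0.2 to 0.3.
- D, the difference in mean change between these people and the rest: 0.5 SD.

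**Step 1: share still unreached after k attempts, (1-p)^k.**

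| p | 3 attempts | 6 attempts | Gap, 3 v 6 | Gap, 4 v 5 |
|---|---|---|---|---|
| 0.2 | 0.512 | 0.262 | 0.250 | 0.410 - 0.328 = 0.082 |
| 0.3 | 0.343 | 0.118 | 0.225 | 0.240 - 0.168 = 0.072 |
| 0.4 | 0.216 | 0.047 | 0.169 | 0.130 - 0.078 = 0.052 |

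**Step 2: difference between arms in missing surveys, f × gap.** For 3 against 6: 0.2 × 0.169 = 0.034 up to 0.3 × 0.250 = 0.075, or 3 to 8 percentage points. For 4 against 5: 0.2 × 0.052 = 0.010 up to 0.3 × 0.082 = 0.025.

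**Step 3: approximate bias, f × gap × D.** For 3 against 6: 0.034 × 0.5 = 0.017 SD up to 0.075 × 0.5 = 0.037 SD. For 4 against 5: about 0.005 to 0.012 SD. Renormalising to the observed participants, bias = D × [(f - m6)/(1 - m6) - (f - m3)/(1 - m3)] with m_k = f(1-p)^k, gives a slightly lower 0.014 to 0.034 SD for 3 against 6.

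**Step 4: against the trial's precision.** With 200 observed per arm, the standard error of a two-arm difference in change is √(2/200) = 0.10 SD. The 3-against-6 bias is then 0.017/0.10 to 0.037/0.10, about 0.2 to 0.4 of a standard error.

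**Wider assumptions.** With f from 0.10 to 0.30, p from 0.1 to 0.3 and D from 3 to 10 T-score points, the renormalised formula for 3 against 6 gives 2 to 7.5 percentage points more missing surveys and a bias of 0.06 to 0.67 T-score points. In each case that is about 2% to 7% of D.

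**The case against.** The rule itself is neutral between arms: the same floor, ceiling and 4-week window apply to every participant. Unequal effort requires staff to use the range differently by arm, and the documents show neither that this happened nor in which direction. That stands, so the point is about what the plan permits.

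A reader might infer that the protocol contradicts itself by capping contacts at 3 in one place and allowing 6 in another. The text does not support that: the 3 is written for missing items in a returned survey, and only the script is carried over to unreturned ones. This is an ambiguity. A reader might also infer that everyone making contact knows the arm. That is certain only for the coach; for research staff it is an inference from the absence of any described blinding.

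There are mitigating provisions. Participants may re-join, surveys can be completed online, on paper or (where accessibility requires) by telephone, reminders may go by email, text or phone, and each completed survey is paid. The last attempt is thus not always the last chance of a return. The appendices cited for withdrawal (12) and for the script (15) are not among the documents and could contain a rule.

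Finally, the 3-against-6 figure is the extreme case, and even that is well under one standard error. This limits the weight of the point but does not remove it, because the remedy is cheap and the SAP states no analytic backstop.

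**Conclusion.** The point holds as a modest weakness in follow-up procedure. The protocol leaves the number of attempts open between 3 and 6, does not require equality across arms, and describes no blinding of those who apply it. It also leaves unclear which limit governs unreturned surveys. Effort to recover outcome data could therefore differ by arm.

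The likely size is small: about 0.02-0.04 SD in the extreme of always 3 against always 6, and 0.005-0.012 SD for 4 against 5. These figures rest entirely on assumed values of p, f and D, on independent attempts and, for the comparison with the standard error, on 200 observed per arm. The bias scales with D, so a larger difference between hard-to-reach and prompt participants would raise it in proportion. The direction is unknown. A reader should not conclude that the comparison is materially biased or that one arm was in fact pursued harder; the documents support neither.

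**What to change.** In Protocol 5.1 and 10.7:
- Set one fixed, logged sequence of attempts for unreturned outcome surveys, identical in all arms and ending only on return, refusal or the last attempt. The six over 4 weeks already allowed would serve; equality matters more than the exact number.
- Count survey contacts separately from session-scheduling contacts, so that not responding about sessions does not by itself end survey follow-up.
- State that the limit of 3 covers only missing items in returned surveys.
- Align the 2-week notice with the sequence.
- Report attempts and returns by arm.

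The cost is protocol wording, a contact log and up to three extra contacts for some late responders, within the maximum already allowed. The SAP was last updated in October 2023 and is partly in the past tense. If data collection is over, the remaining step is to report attempts and returns by arm so far as they were recorded. A missing-data method in the SAP is a separate need that this change does not replace.

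### The staff-withdrawal rule can end outcome follow-up for silence about sessions, a trigger that exists in the two active arms but not in TAU

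*Protocol*

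**What the plan says.** Protocol 5.1, under Withdrawal from study, sets one rule for everyone. After contact by phone or email "no fewer than 3 times and no more than 6 times over a 4-week period", people who stay non-responsive "to attempts by research staff and the wellness coach to schedule visits or follow up on survey mailings will be withdrawn from this study". Late in the sequence they are warned: "we will let participants know that we'll conclude their participation if we do not hear back within 2 weeks". The way back is at the participant's initiative: "if they would like to re-join the study, then they can contact us at their convenience". Section 10.7 repeats the rule and opens with "We will withdraw enrolled participants who are unreachable after multiple attempts". The form's question there asks about partial withdrawal with continued data collection; the answer describes none.

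What there is to be silent about differs by arm (5.1, Groups 1 to 3):

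- **EW-D:** 8 sessions are expected, and up to 10 are allowed.
- **Education:** 8 sessions, also given by a Wellness Coach, who is called the social worker in this arm.
- **TAU:** "participants in the TAU arm will not receive contact with a study social worker".

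All arms have outcome surveys (Appendix 8) at baseline, before randomization, and at 3, 7 and 12 months. One further form is specific to an arm: "Participants in the EW-D arm (group 1) will complete an additional survey designed to assist the Wellness Coach with tailoring the intervention sessions" (Appendix 9, on paper or by telephone, at four time points). The missing-data paragraph covers both forms, and of its script it says: "This script will also be used to remind participants about unreturned surveys and consent forms".

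People who withdraw themselves are asked whether they would still complete parts of the study, such as the surveys. No such offer is described for people withdrawn by staff. The SAP (Statistical Approach) states intent-to-treat and an ANOVA on change scores, and gives no method for missing outcomes.

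**The concern.** The rule links two things that should be separate: stopping the sessions and stopping outcome measurement. Take someone who goes quiet about sessions at month 4, ignores the attempts and the warning, and would still have returned the later outcome surveys. In EW-D or education the text allows that person's participation to be concluded. In TAU no session is being scheduled at month 4, so the same person simply receives the next survey.

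If this happens often enough, the active arms lose their less engaged members by rule while TAU keeps them. Those who remain in EW-D and education are then selected on engagement, and comparisons with TAU are no longer protected by randomization. A participant with no later survey has no change score. The ANOVA therefore drops that participant, despite the intent-to-treat statement.

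**Working it through.** Neither document gives a dropout rate, an SD or a power calculation, so there is no figure of the plan's own to reproduce. The check counts triggers from the text and then uses labelled assumptions to show scale.

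**1. Planned events after randomization at which silence could lead to withdrawal**

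| | EW-D | Education | TAU |
|---|---|---|---|
| Sessions | 8 | 8 | 0 |
| Outcome surveys | 3 | 3 | 3 |
| Total | 11 | 11 | 3 |

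The 8 EW-D sessions agree with the printed timing (2×2 + 4×1 = 8). The printed education timing adds up to 2 + 5 = 7, not the stated 8. That should be reconciled separately; here it would change 11 to 10. The SAP puts the middle survey at 6 months and the protocol at 7, but the count is 3 either way. The 12-month GPS week is planned equally in each arm and is left out.

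If the EW-D-only survey is also a trigger, EW-D has 11 + 4 = 15 events, or 12 if its 3-, 7- and 12-month copies share a mailing with the outcome survey.

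**2. Loss.** Assume that each event carries the same independent chance q of ending in withdrawal. Loss = 1 − (1 − q)^k for k events.

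| q (assumed) | 11 events | 3 events | Difference |
|---|---|---|---|
| 0.5% | 5.4% | 1.5% | 3.9 points |
| 1% | 10.5% | 3.0% | 7.5 points |
| 2% | 19.9% | 5.9% | 14.1 points |
| 5% | 43.1% | 14.3% | 28.9 points |

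(Differences are taken before rounding.)

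The SAP's primary-outcome entry names no time point for the change score. If it is the post-intervention survey, the events before it are 8 + 1 = 9 in the active arms and 1 in TAU. At q = 1% the loss is 8.6% v 1.0%, and at 2% it is 16.6% v 2.0%. The differences of 7.6 and 14.6 points are close to those above.

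**3. Shift in EW-D minus TAU.** Assume that those lost would have changed by 3 T-points less than those kept. Shift = 3 × difference in loss.

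- q = 1%: 3 × 0.075 = 0.22
- q = 2%: 3 × 0.141 = 0.42
- Over the wider range: 0.12 at q = 0.5% and 0.87 at q = 5%

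Education minus TAU shifts by the same amount, and EW-D minus education by zero.

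**4. Effect on the SAP's omnibus test.** Assume a change-score SD of 8 and 200 per arm (600 in three arms; the ratio is not stated). With two arms shifted by δ against the third, the noncentrality is λ = 200 × (2/3) × δ² / 8² = 2.08 δ².

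- δ = 0.225: λ = 0.105, rejection 5.8%
- δ = 0.421: λ = 0.370, rejection 7.9%

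Both use F(2, 597) at the 5% level. With the retained numbers (about 179/179/194 and 160/160/188), the rates are 5.7% and 7.5%.

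**5. After the fix.** With only the 3 outcome surveys as triggers, every arm has 3 events. On the same assumptions loss is 3.0% at q = 1% and 5.9% at q = 2% in all arms, and the shift is zero.

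**The case against.** The strongest reply is that the rule is about unreachable people. It names research staff and the coach together, requires repeated attempts over 4 weeks, warns before acting and lets people return. Someone who answers that they want no more sessions falls under the self-withdrawal text and is asked about continuing surveys. If silence to both contacts is needed, a person who ignores the coach but answers research staff stays in. This stands as a reason to expect fewer such withdrawals. It does not remove the problem. The two kinds of contact attempt are joined by *or*, TAU has no coach, and between the 3- and 7-month surveys session scheduling is the main contact due. If a narrower rule was meant, the text does not say so.

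Three stronger readings are tempting, and the documents do not support them:

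- **That the EW-D-only survey is a trigger, so all three arms differ greatly.** Appendix 9 may count as a survey mailing, and it shares the reminder script, but the withdrawal rule does not name it. Without it EW-D and education are equal at 11; with it they are at most 15 v 11. Its use at 7 and 12 months is not idle either: 5.1 says the responses also build the intervention owner's supporting data.
- **That arm-dependent loss or a bias favouring EW-D is established.** No dropout figures are given. Silence probably clusters within people: someone who ignores several contacts about sessions may ignore surveys too, which makes the excess caused by the rule smaller than the independence formula gives. If those lost would have changed more, the sign reverses.
- **That false EW-D v TAU findings rise from 5% to 7% to 12%.** That comes from an unadjusted pairwise test on 15 v 3 events. The SAP uses ANOVA and then Tukey. Even on 15, 11 and 3 events, this gives about 3% (q = 1%) and 5% (q = 2%) for that contrast, against about 1.7% with no bias.

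A last objection is timing. The SAP is dated October 2023 and written largely in the past tense, so a protocol change may come too late to recover data. That affects the remedy, not the point.

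**Conclusion.** The point holds in a limited form. As written, the rule can end outcome follow-up for silence about sessions. That trigger exists in EW-D and education and cannot occur in TAU, and no stated retention step or analysis method makes up for it. The exposure is active arms against TAU, about 11 events against 3. Between EW-D and education it is nil unless Appendix 9 counts.

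On the stated assumptions the shift is 0.2 to 0.4 T-points, or 0.03 to 0.05 of the assumed SD, with omnibus error of about 6% to 8%. Every input to that size except the event counts and the total of 600 is assumed, and clustering would reduce it. It is a foreseeable and modest risk, not a demonstrated bias. It is worth correcting because the correction is cheap and makes follow-up consistent with the intent-to-treat statement.

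**What to change.** In 5.1, 10.7 and Appendix 12, state that:

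- loss to follow-up is declared only for non-response about the common outcome survey (Appendix 8), with the same trigger in every arm;
- silence about sessions ends session scheduling only;
- non-return of Appendix 9 ends reminders for that form only;
- outcome surveys continue to be sent at 3, 7 and 12 months in either case.

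The cost is a short protocol modification and some extra survey reminders to people who have ignored their coach.

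If follow-up is already complete, report staff-initiated withdrawals by arm and by trigger (session scheduling, outcome survey, Appendix 9), so that readers can see whether loss differed between the active arms and TAU. This needs only the study's own contact and withdrawal records.

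### The SAP's change-score ANOVA names no visit for the patient-reported outcomes and has no missing-data method, so it does not deliver the stated intent-to-treat analysis

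*Protocol*

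**What the plan says.** **SAP.** The Statistical Approach commits every analysis to intent-to-treat but does not define the analysis set. For each primary and secondary outcome it compares change scores between the three arms with an ANOVA, followed by Tukey's HSD if the omnibus test is significant, at a two-sided 0.05 level. It gives no imputation, repeated-measures model, missingness assumption or sensitivity analysis. The primary outcome is change in the PROMIS Ability to Participate T score, with no visit attached. The secondary patient-reported changes have no visit either. The SAP's assessment timeline has follow-up surveys at 3, 6 and 12 months and GPS data at baseline and 12 months only.

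**Protocol, surveys.** Section 5.1 says: "All 3 groups will complete a baseline (prior to intervention), 3-month (mid-intervention), 7-month (post-intervention), and 12-month survey". Its paragraph on missing data covers retrieval of missing items and reminders about unreturned surveys. These are collection steps, not an analysis method.

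**Protocol, withdrawal.** Sections 5.1 and 10.7 provide that participants non-responsive to "attempts by research staff and the wellness coach to schedule visits or follow up on survey mailings will be withdrawn from this study". Contact is attempted "no fewer than 3 times and no more than 6 times over a 4-week period". Staff say that they will "conclude their participation if we do not hear back within 2 weeks", and participants are told that "if they would like to re-join the study, then they can contact us at their convenience". Section 10.7 opens: "We will withdraw enrolled participants who are unreachable after multiple attempts". People who withdraw themselves are asked "if they would be willing to continue completing any aspect of the study going forward, such as the study surveys". Appendix 12, cited for the staff rule, is not in the available text.

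**Numbers.** Section 2.1 treats 600 as the number completing and requests approval for 750. The GPS text in 5.1 treats 600 as the number enrolled.

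**The concern.** A change score needs both a baseline and a follow-up value. With no rule for a missing follow-up, an ANOVA on change scores can include only people who have the score at the visit tested. Someone randomized who returned the 3-month survey and nothing later contributes nothing to a 12-month test. That is an available-case analysis under an intent-to-treat label.

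The missing visit name makes this worse. There are three follow-up surveys and therefore three candidate primary changes. The documents do not fix which one is the primary test, nor whose missing score removes them from it. The SAP declines a multiplicity adjustment because there is one primary outcome, and that reasoning presumes one visit. The conflict between 6 and 7 months leaves even the list of visits unsettled.

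The SAP also uses the baseline inefficiently. Subtracting it fixes its coefficient at 1, whereas adjustment estimates the coefficient.

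The withdrawal rule is a secondary matter. It is a foreseeable source of missing scores, and the available text plans no later surveys for these people unless they make contact themselves.

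**Working it through.** The documents give no power calculation, SD, between-visit correlation or loss rate, so there is no planned figure to reproduce. The variance figures below rest on assumptions and are large-sample results.

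**Assumptions.** Equal SD *s* at every visit; the same correlation *r* between all visits, 0.5 to 0.8; a fraction *f* of each arm lacking the final score at random, 5% to 20%; *k* = 0, 1 or 2 earlier follow-up surveys held by those people; *n* randomized per arm.

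**Step 1: baseline adjustment, observed scores only.**
- Variance of an arm's mean change: 2*s*²(1 − *r*) / [*n*(1 − *f*)].
- Variance with baseline adjustment: *s*²(1 − *r*²) / [*n*(1 − *f*)].
- Ratio: (1 + *r*)/2, which does not depend on *f*.
- *r* = 0.5: 1.5/2 = 0.75, variance 25% lower, equivalent to 1/0.75 = 1.33, or 33% more participants.
- *r* = 0.8: 1.8/2 = 0.90, variance 10% lower, equivalent to 1/0.90 = 1.11, or 11% more participants.

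**Step 2: further gain from earlier surveys.** Given baseline, two follow-ups correlate at *q* = *r*/(1 + *r*). The share of final-score variance that *k* earlier follow-ups explain is R² = *kq*²/[1 + (*k* − 1)*q*]. The mixed-model variance is *s*²(1 − *r*²)/*n* × [R² + (1 − R²)/(1 − *f*)]. Divided by the baseline-adjusted variance in Step 1, this is 1 − *f*R². The further reduction is therefore *f* × R².

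| *r* | *q* | *k* | R² | *f* = 5% | *f* = 20% |
|---|---|---|---|---|---|
| any | – | 0 | 0 | 0% | 0% |
| 0.5 | 0.333 | 1 | 0.111 | 0.6% | 2.2% |
| 0.8 | 0.444 | 1 | 0.198 | 1.0% | 4.0% |
| 0.5 | 0.333 | 2 | 0.167 | 0.8% | 3.3% |
| 0.8 | 0.444 | 2 | 0.274 | 1.4% | 5.5% |

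With at most one earlier follow-up the range is 0% to 4.0%. The 5.5% needs both earlier surveys, so it describes people who miss only the last one.

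**Step 3: what the withdrawal rule forgoes.** Of the three follow-ups at 3, 7 and 12 months, withdrawal at the 3-month survey forgoes two of three and leaves *k* = 0. Withdrawal at the 7-month survey forgoes one of three and leaves *k* of at most 1. For these people the first three rows of the table apply.

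**Step 4: how many would be left out.** If 600 is the number enrolled (5.1, GPS text), 5% to 20% is 0.05 × 600 = 30 to 0.20 × 600 = 120 people. If 600 is the number completing (2.1), 750 × 0.80 = 600, so even a 20% loss would already be covered. The 20% is inferred from those two numbers and is not stated.

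**The case against.** **The SAP never says complete-case.** True. The exclusion is inferred from what is specified and what is left out. Some handling might be intended, but none is written, and reminders to participants do not supply it.

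**Most of the gain has nothing to do with missing data.** This stands. The 10% to 25% in Step 1 would be the same with full follow-up. A reader might add the two gains and credit the sum to missing data. Only the Step 2 part belongs there, and it is small.

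**The 750 may cover the loss.** This stands for numbers, on the reading in Protocol 2.1. It does not name a visit or protect against selective loss.

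**The withdrawal rule is reasonable.** Largely so. It covers people unreachable after 3 to 6 contacts, with notice and an open route back. The contrast with self-withdrawers carries little weight, because someone who does not answer cannot be asked to continue surveys. Appendix 12 may say more.

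**A stronger reading is tempting.** Because "participants in the TAU arm will not receive contact with a study social worker", a reader might infer that session scheduling causes more withdrawal in the two contact arms and so biases the comparison with TAU. The documents do not support this. The wording does not clearly make coach non-response alone a trigger, survey non-response applies in every arm, and no loss rate or outcome difference is given. Size and direction cannot be derived.

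**A new primary model now could be post hoc.** This stands. The SAP was last updated in October 2023 and says in the past tense that ANOVAs were used. The fix allows for it.

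**The visit point does not reach the GPS outcomes.** Correct. They have one follow-up, at 12 months.

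**Conclusion.** The concern holds as a defect of the SAP and should be fixed. Three facts come straight from the documents: no missing-data method, no visit for the primary or other patient-reported changes, and 6 months in the SAP against 7 in the protocol. It follows that the ANOVA as written leaves out randomized participants who lack the tested visit's score and discards their other surveys.

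The precision at stake is moderate and depends on the assumed correlations. It comes mainly from baseline adjustment (equivalent to 11% to 33% more participants); what earlier surveys add is small. Whether the loss comes out of 600 is unresolved in the protocol.

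The withdrawal rule is secondary. In the available text no later surveys are planned for people whom staff withdraw as unreachable, unless they make contact. The documents show no bias from this, and none is claimed. Confidence is moderate.

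**What to change.** 1. **SAP, patient-reported outcomes.** Name the primary visit and reconcile 6 with 7 months. Analyse these outcomes with a baseline-adjusted, likelihood-based mixed model (arm by visit) on all available surveys from all randomized participants. Keep the omnibus test, followed by adjusted pairwise contrasts, at the named visit. Add a delta-adjusted sensitivity analysis by arm.
2. **SAP, GPS outcomes.** Adjust for baseline. With a single follow-up, that is the only gain available.
3. **If the ANOVA has already been run.** Keep it reported as the primary analysis and present the mixed model as an additional analysis, labelled and dated.
4. **Reporting.** Show staff withdrawals by arm.
5. **Only if follow-up is still open.** Amend Protocol 5.1 and 10.7 so that the remaining scheduled surveys go to every randomized participant who has not refused contact.

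**Cost.** Items 1 to 4 need some analysis work on data already held. The mixed model relies on missing at random; the delta analysis shows how far departures from it would change the result. Item 5 needs a short amendment, a few mailings and, at $25 per survey (Protocol 4.4), at most 2 × $25 = $50 per withdrawn participant. If follow-up is closed, item 5 falls away.
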